### 5.5 Reporting Conventions

The following conventions will be used across all study summaries and analyses, unless otherwise specified in the corresponding section.

- Summary statistics will consist of sample size (n), mean, standard deviation (SD), median, minimum (min), and maximum (max) values for continuous and some ordinal variables; and sample size (n), frequencies, and percentages (%) for categorical and some ordinal variables.
- Statistical tests and confidence intervals (CI) will be two-sided unless otherwise specified; statistical tests will use an alpha threshold of 0.05 and CIs will use 95% confidence unless otherwise specified.
- Mixed Models for Repeated Measures (MMRM) will be fit using the unstructured covariance matrices. In the event of lack of model convergence, other covariance structures may be used.
- P-values will be calculated to three decimal places. P-values less than 0.001 will be presented as "< 0.001."

Unless otherwise specified, descriptive summary tables will be structured with a column for each monotherapy group (ZOF 30 mg or AML 5 mg) or combined treatment group (ZOF/AML 30/5 mg or ZOF/AML 30/10 mg) and overall (All Patients) and will include the total population size for each group in the header. Conversely, inferential summary tables will use only the All Patients column, unless otherwise specified, to prevent overinflation of the type I error rate.

For descriptive summary tables, patients will be classified as either ZOF/AML 30/5 mg or ZOF/AML 30/10 mg such that no patients are counted in both groups. That is, even though patients in the ZOF/AML 30/10 mg group are also exposed to the ZOF/AML 30/5 mg treatment, they will only be included in the ZOF/AML 30/10 mg and All Patients columns within the summary tables, and not within the ZOF/AML 30/5 mg column.

Summary tables will also indicate the number of patients with complete data for each measurement, event, or outcome.

Data listings will be sorted by treatment group, patient, and visit (when applicable).

### 5.6 Missing Data

### 5.6.1 Imputation of Blood Pressure Data

Missing blood pressure values that occur after baseline will be imputed for the sensitivity analysis using Last Observation Carried Forward (LOCF). Any missing data for blood pressure at baseline will not be imputed. No other standard imputations of missing efficacy data will be applied.

### 5.6.2 Imputation of Adverse Event Start Dates

Partial start dates for Adverse Events (AEs) are imputed as detailed below in order to classify each AE as treatment-emergent, as defined in section 8.2.

Start date:

- If start date is completely missing, start date is set to date of first dose.
- If (1) year is present and month and day are missing or (2) year and day are present and month is missing:
  - If year = year of first dose, then set month and day to month and day of first dose.
  - If year < year of first dose, then set month and day to December 31st.
  - If year > year of first dose, then set month and day to January 1st.
- If month and year are present and day is missing:

- If year = year of first dose and
  - If month = month of first dose, then set day to day of first dose date.
  - If month < month of first dose, then set day to last day of month.
  - If month > month of first dose, then set day to 1st day of month.
- If year < year of first dose, then set day to last day of month.
- If year > year of first dose, then set day to 1st day of month.

### 5.6.3 Imputation of Prior/Concomitant Medication Start and Stop Dates

Partial start and end dates for medications are imputed as detailed below in order to classify each medication as either prior or concomitant, as defined in section 6.5.

Start date:

- If start date is completely missing, start date will be imputed with the informed consent date.
- If year is present and month and day are missing, set month and day to January 1.
- If year and day are present and month is missing, set month and day to January 1.
- If year and month are present and day is missing, set day to the 1st day of month.

Stop date:

- If end date is completely missing, end date will not be imputed and medication will be assumed to be ongoing.
- If year is present and month and day are missing, set month and day to December 31st.
- If year and day are present and month is missing, set month and day to December 31st.
- If year and month are present and day is missing, set day to the last day of month.

### 5.7 Interim Analyses and Data Monitoring

There will be no interim analyses for this study.

### 5.8 Multi-Center Studies

Approximately 31 study centers will be used to enroll patients into this study. All sites will be pooled and analyzed collectively, except for the sensitivity analysis for the primary efficacy endpoint which is described in section 7.2.2 of this SAP.

### 5.9 Multiple Testing

The current study has a single primary efficacy endpoint. The secondary efficacy endpoints are derived from the primary objective and will be used to support the conclusion of the primary efficacy endpoint, provided that the primary efficacy endpoint is met. Thus, adjustments for multiple testing in the secondary efficacy endpoints will not be applied.

### 6 Summary of Study Data

### 6.1 Patient Disposition

Patient disposition parameters including the number of patients screened, screen failures, enrolled, completed monotherapy period, completed combined treatment period, completed the study, discontinued the study, and reason for discontinuation will be summarized combined treatment group (ZOF/AML 30/5 mg or ZOF/AML 30/10 mg) and All Patients for the FAS population.

A by-patient data listing of study completion information, entry criteria violations, and the reason for study discontinuation will be presented for the FAS population.

### 6.2 Protocol Deviations

A list of protocol deviations (PD) will be prepared for the final statistical analysis and protocol deviations will be classified as major or minor by the sponsor in coordination with the study statistician based on their potential impact on the data quality and integrity. Critical deviations will be classified as Major for purposes of defining the PP population. Major protocol deviations will be specified prior to database lock and will include protocol deviations that may impact the primary efficacy endpoint.

All protocol deviations will be discussed and reviewed on a case-by-case basis before the DBL. All PDs authorized by Sponsor will be documented.

Individual PDs will be presented in a by-patient data listing for the FAS population who have at least one deviation. The number and percentage of patients with PDs will be summarized by deviation on the FAS population. Additional Major and Minor PDs may be identified during data review and will be reflected in the Table and Listing as appropriate.

All PDs will be recorded and classified in Clinical Trial Management System (CTMS).

### 6.3 Demographic and Baseline Variables

Demographic and baseline characteristics including study site, age, sex, race, ethnicity, height (cm), weight (kg), BMI (kg/m2), smoking status (including e-cigarette use), select medical history (hypertension grade 1 or 2, presence/absence of Diabetes, presence/absence of Hypercholesterolemia), and treatment at run-in will be summarized by combined treatment group (ZOF/AML 30/5 mg or ZOF/AML 30/10 mg) and All Patients for the SAF population.

A by-patient data listing of demographic and baseline characteristics will also be presented for the SAF population.

### 6.4 Medical History

Medical History will be coded using the Medical Dictionary for Regulatory Activities (MedDRA) version 24.1 or later. Medical history will be presented in a by-patient data listing for the SAF population and will include the System Organ Class (SOC) and Preferred Term (PT) for each medical condition.

### 6.5 Prior and Concomitant Medications

Prior and concomitant medications will be coded using the World Health Organization Drug Dictionary (WHO-DD) version Sep 2021 or later. Concomitant procedures will be coded using MedDRA version 24.1 or later.

Prior medication is defined as any medication taken within 30 days prior to the start of the study which has a stop date prior to the date of first dose of monotherapy (ZOF 30 mg or AML 5 mg). Concomitant medication is defined as any medication with a start date on or before the date of *last* dose of study drug and is ongoing or has a stop date on or after date of *first* dose of monotherapy (ZOF 30 mg or AML 5 mg).

Prior and concomitant medications will be summarized separately by Anatomic Therapeutic Class (ATC) Level 1 and Preferred Term by combined treatment group (ZOF/AML 30/5 mg or ZOF/AML 30/10 mg) and All Patients for the SAF population. That is, all patients in the SAF population who took at least one prior/concomitant medication will be summarized together in the All Patients column of the corresponding summary tables. All patients who take ZOF/AML 30/10 mg will be summarized in the ZOF/AML 30/10 mg column, even for medications they took in the monotherapy period or while taking the ZOF/AML 30/5 mg regimen. Lastly, all patients who take ZOF/AML 30/5 mg for the duration of the combined therapy period will be summarized in the ZOF/AML 30/5 mg column, even for medications they took in the monotherapy period.

Patients taking the same medication multiple times will be counted once per medication. Prior and concomitant medications as well as concomitant procedures will be presented in by-patient data listings for the SAF population.

### 7 Efficacy Analyses

All efficacy analyses will be performed on the Efficacy population (EFF) unless otherwise specified. Monotherapy: visit 2 (week 0) efficacy analysis (number and proportion of patients achieving the BP goal (sitting BP≤130/80 mmHg) at Visit 2) will be performed on the Full Analysis Set (FAS population). Results will be presented as described in section 5.5. In addition to the inferential analyses discussed in the subsections below, descriptive analyses will be performed to summarize the observed and change from baseline values for mean sitting SBP and DBP for all study visits. All blood pressure parameters will also be presented in a by-patient data listing for the safety (SAF) population.

### 7.1 Efficacy Variable Derivations

### 7.1.1 Blood Pressure (BP) Goal (Controlled v Uncontrolled)

Multiple endpoints (2.3, 3.3, and 3.4) involve patients meeting the BP goal of sitting  $BP \le 130/80$  mmHg at Visit 2 (Week 0), Visit 3 (Week 4) and Visit 4 (Week 8).

A patient will be considered to have met the BP goal (controlled BP) if their SBP  $\leq$  130 mmHg AND their DBP  $\leq$  80 mmHg. If a patient meets one of these criteria but not the other, then they will not be considered to have met the BP goal. That is, a patient's BP is considered uncontrolled if their SBP > 130 mmHg OR their DBP > 80 mmHg.

### 7.2 Primary Efficacy Analyses (Endpoint 1.1)

### 7.2.1 Primary Analysis

Endpoint 1.1: Change in mean sitting DBP between Visit 2 (Week 0) and Visit 4 (Week 8).

Endpoint 1.1 will be analyzed using a paired t-test with a type I error rate of 0.05 to test the null hypothesis that the mean change in DBP is 0 mmHg against a two-sided alternative.

The observed values for sitting DBP will be summarized at Baseline (Visit 2) and Visit 4. The change from Baseline to Visit 4 values will be assessed using the paired t-test as described above and will present the mean, SD, min, max, critical t-value, degrees of freedom (df), 95% confidence internal (CI) and p-value. If resulting p-value  $\leq 0.05$ , the null hypothesis will be rejected, and we will conclude that the mean sitting DBP at Visit 4 is significantly different from that at Baseline. Conversely, if p-value > 0.05, then we will

fail to reject the null hypothesis and we cannot conclude a significant difference between mean sitting DBP at Baseline and Visit 4.

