12.1 Statistical Methods (Blinding and Randomization)

This is a non-randomized, unblinded study. Unless specified otherwise, all statistical testing will be two-sided and will be performed using a significance (alpha) level of 0.05.

MENARINI	Corporate Medical Department		ent
Identification Number	Version Number	State	Effective date
FORM-000050125	2.0, CURRENT	Effective	08, Jan 2021

Sponsor: Menarini International Operations Luxembourg SA Study Code: MEIN/20/ZoAm-Hyp/001	Protocol Version 1.0 of 1	23/04/2021

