12.2 Determination of Sample Size

A total sample size of 216 patients is required to achieve 90% power at a 5% significance level assuming a difference in mean DBP from baseline (Visit 2) to 8 weeks (Visit 4) of 4 mmHg and a standard deviation (SD) for this difference of 10 mmHg. The mean change in DBP for the null hypothesis is set equal to 2 mmHg. To achieve this, a total of 290 patients will be enrolled, allowing for a 25% withdrawal rate.

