12.4 Analysis Variables

The primary endpoint (i.e. change in sitting Diastolic Blood Pressure from Visit 2 to Visit 4) and primary statistical analysis specifications will be detailed in 12.5.2. Secondary endpoints and their respective statistical analyses are summarized in 12.5.4 while safety analyses in 12.5.7. Data handling and imputation methods are reported in 12.5.9.

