12.5.2 Primary (efficacy) analysis

For the primary efficacy analysis of the primary endpoint, the change in sitting Diastolic Blood Pressure (DBP) from Visit 2 to Visit 4 will be assessed using a paired t-test. A Type I error

MENARINI	Corporate Medical Department		
Identification Number	Version Number	State	Effective date
FORM-000050125	2.0, CURRENT	Effective	08, Jan 2021

Sponsor: Menarini International Operations Luxembourg SA Study Code: MEIN/20/ZoAm-Hyp/001	Protocol Version 1.0 of 1	23/04/2021

threshold of 0.05 will be used to test the null hypothesis that the mean reduction in DBP is 0 mmHg against a two-sided alternative. The Efficacy population will be used to analyse the primary endpoint.

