### 4.6 Sample Size

A total sample size of 216 patients is required to achieve 90% power at a 5% significance level

assuming a difference in mean DBP from baseline (Visit 2) to 8 weeks (Visit 4) of 4 mmHg and a standard deviation (SD) for this difference of 10 mmHg. The mean change in DBP for the null hypothesis is set equal to 2 mmHg. The alternative hypothesis is that the mean change in DBP is greater than 2 mmHg. To achieve this sample size, a total of 290 patients will be enrolled, allowing for a 25% withdrawal rate.

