[2] SD = Standard Deviation. CI = Confidence Interval. df = degrees of freedom.

 [3] Visit 4 CFB results are generated using paired t-test with alpha = 0.05 to evaluate if the mean change in diastolic blood pressure (DBP) from Baseline (Visit 2) to Visit 4 is significantly different from 0.
 Source: Listing 16.2.6
 Program Name: XXXX.SAS
 Date: DDMMMYYYY

- Repeat for the following tables:
  - o 14.2.2.2 Summary of Change in Mean Sitting Diastolic Blood Pressure (DBP) from Visit 2 to Visit 4 Per Protocol Population
    - Change column header from "EFF" to "PP"
  - o 14.2.2.3 Summary of Change in Mean Sitting Diastolic Blood Pressure (DBP) from Visit 2 to Visit 4 Using LOCF Efficacy Population
    - Add footnote to statistic column "[4] Missing blood pressure (BP) values that occur after Baseline (Visit 2) are imputed using Last Observation Carried Forward (LOCF)."
  - o 14.2.2.4 Summary of Change in Mean Sitting Diastolic Blood Pressure (DBP) from Visit 2 to Visit 4 by Study Site Efficacy Population
    - Use of SAS #byar/#byval will produce this table separately for each study site within the same output file.
  - o 14.2.3.1 Summary of Change in Mean Sitting Systolic Blood Pressure (SBP) from Visit 2 to Visit 4 Efficacy Population

		All Patier	nts (N=xx)	
Visit [1]	Statistic [2,3]	Male	Female	
Baseline (Visit 2)	n	xx	XX	
	Mean (SD)	xx.x (xx.xx)	xx.x (xx.xx)	
	Median	XX.X	XX.X	
	Min, Max	xx, xx	хх, хх	
Visit 4	n	хх	хх	
	Mean (SD)	xx.x (xx.xx)	xx.x (xx.xx)	
	Median	xx.x	xx.x	
	Min, Max	xx, xx	хх, хх	
Visit 4 CFB	n	хх	хх	
	Mean (SD)	xx.x (xx.xx)	xx.x (xx.xx)	
	Min, Max	xx, xx	xx, xx	
	t-value (df)	x.xx (x)	x.xx (x)	
	95% CI	(xx.x, xx.x)	(xx.x, xx.x)	
	p-value	x.xxx	x.xxx	

Table 14.2.2.5 Summary of Change in Mean Sitting Diastolic Blood Pressure (DBP) from Visit 2 to Visit 4 by Gender (Efficacy Population)

[1] CFB = Change from Baseline.

[2] SD = Standard Deviation. CI = Confidence Interval. df = degrees of freedom.

[3] Visit 4 CFB results are generated using paired t-test with alpha = 0.05 to evaluate if the mean change in systolic (SBP; endpoint 2.1) or diastolic blood pressure (DBP; endpoint 1.1) from Baseline (Visit 2) to Visit 4 is significantly different from 0.

Source: Listings 16.2.4.1, 16.2.6 Program Name: XXXX.SAS

Date: DDMMMYYYY

- Repeat for the following tables:
  - o 14.2.2.6 Summary of Change in Mean Sitting Diastolic Blood Pressure (DBP) from Visit 2 to Visit 4 by Age Group Efficacy Population

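### The trial is sized against a 2 mmHg null but tested against 0 mmHg, so the stated 90% power belongs to a test the plan does not run

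*SAP*

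**What the plan says.** **Sizing text.** The synopsis, Protocol 12.2 and SAP 4.6 all ask for 216 patients for 90% power at 5%, assuming a mean DBP change of 4 mmHg from Visit 2 to Visit 4 with SD 10. All three add: "The mean change in DBP for the null hypothesis is set equal to 2 mmHg". Only SAP 4.6 gives a direction: "The alternative hypothesis is that the mean change in DBP is greater than 2 mmHg".

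**Analysis text.** Protocol 12.4 says that the "primary statistical analysis specifications will be detailed in 12.5.2", and that section uses a paired t-test at 0.05 to "test the null hypothesis that the mean reduction in DBP is 0" mmHg against a two-sided alternative. SAP 7.2.1 does the same: "to test the null hypothesis that the mean change in DBP is 0 mmHg against a two-sided alternative". The table shells follow. Footnote 3 of Table 14.2.2.1 asks whether the "mean change in diastolic blood pressure (DBP) from Baseline (Visit 2) to Visit 4 is significantly different from 0", and footnote 3 of Table 14.2.2.5 also uses 0.

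**General rule.** Under Protocol 12.1, unless specified otherwise, "all statistical testing will be two-sided and will be performed using a significance (alpha) level of 0.05". SAP 5.5 also makes two-sided testing the default.

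The primary objective (SAP 3.1.1) names no 2 mmHg margin. SAP section 10, which lists departures from the protocol, does not mention the difference.

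**The concern.** The analysis passages agree with one another, and so do the sizing passages, but the two sets describe different hypotheses. The conflict lies inside each document, not only between protocol and SAP.

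A reader of the sizing text would take a positive trial to mean a fall shown to exceed 2 mmHg. SAP 7.2.1 would conclude only that Visit 4 differs from Baseline. The verdict carries further, because SAP 5.9 lets the secondary endpoints, unadjusted for multiplicity, support the primary conclusion only if the primary endpoint is met. In an open-label, non-randomised before-after study, the pass mark should not be open to two readings once data are in hand.

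**Working it through.** **Inputs** (Protocol 12.2, SAP 4.6): n = 216, SD of the change 10 mmHg, assumed true fall 4 mmHg, alpha 5%, target power 90%. Sizing null 2 mmHg; analysis null 0 mmHg.

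**Reproducing 216.** Normal approximation: n = (SD × (z_alpha + z_power) / (true − null))².

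- Null 2, one-sided 5%: (10 × (1.645 + 1.282) / 2)² = 214.1
- Null 2, two-sided 5%: (10 × (1.960 + 1.282) / 2)² = 262.7
- Null 0, two-sided 5%: (10 × (1.960 + 1.282) / 4)² = 65.7

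The exact noncentral t (df = n − 1, noncentrality = (true − null) / (SD/√n)) gives 216, 265 and 68. For the one-sided test of 2 mmHg, n = 215 gives 0.8995 and n = 216 gives 0.9007, so that test reproduces the plan's figure exactly. A one-sided test of 0 would need 55. Inflating for 25% gives 216/0.75 = 288, consistent with the stated 290.

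**Pass marks at n = 216.** SE = 10/√216 = 0.680. The critical t on 215 df is 1.971 two-sided and 1.652 one-sided.

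| Test | Observed fall needed (mmHg) | Power at true 4 mmHg | n for 90% |
|---|---|---|---|
| Planned: null 0, two-sided | 1.971 × 0.680 = 1.34 | 0.99995 | 68 |
| Sized: null 2, one-sided 5% | 2 + 1.652 × 0.680 = 3.12 | 0.901 | 216 |
| Null 2, two-sided 5% | 2 + 1.971 × 0.680 = 3.34 | 0.833 | 265 |

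An observed fall between 1.34 and 3.12 mmHg therefore passes the planned test and fails the sized one. Against 0 two-sided, 216 patients give 90% power for a true fall of 2.2 mmHg.

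**How often the verdicts differ.** Any result that passes the sized test also passes the planned one, so the chance of disagreement is the difference in power:

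- True fall 4 mmHg: 0.99995 − 0.9007 = 0.10
- True fall 3 mmHg: 0.9924 − 0.4287 = 0.56
- True fall 2 mmHg: 0.8330 − 0.0500 = 0.78

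If the true fall equals the sizing null of 2 mmHg, the planned test still declares success 83% of the time.

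**Sensitivity to SD.** The two thresholds scale with the observed SD: 0.8 × 1.341 = 1.07 and 2 + 0.8 × 1.124 = 2.90 mmHg at SD 8; 1.2 × 1.341 = 1.61 and 2 + 1.2 × 1.124 = 3.35 mmHg at SD 12.

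**Sensitivity to loss after Visit 2** (assumed 5% to 25%; the documents give no separate rate). Protocol 5.1 uses the 25% allowance to get from 290 screened to 216 starting the assessment period, although Protocol 12.2 and SAP 4.6 could be read as covering all withdrawals. With n from 205 down to 162:

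- Planned pass mark: 1.38 to 1.55 mmHg
- Planned-test power: still at least 99.9%
- One-sided power against 2 mmHg: 89% to 81%
- Two-sided power against 2 mmHg: 81% to 72%

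**The case against.** The best defence is that the decision rule is already settled. Protocol 12.4 points to 12.5.2 for the primary specification. Protocol 12.5.2, SAP 7.2.1 and the shells then give one complete rule, and SAP 7.2.1 spells out the conclusion on either side of p = 0.05. Its type I error is controlled, its power is ample, and a null of 0 suits an objective of lowering pressure. The 95% confidence interval will be reported, so anyone can compare the result with 2 mmHg. On this view the disagreement probabilities set the planned test against one that no analysis section schedules, and only a sizing justification needs correcting.

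Much of that stands. The planned test is valid and well powered, and the disagreement probabilities matter only if 2 mmHg was the intended bar, which the documents do not settle. But the 2 mmHg null is no slip of the pen, because it generated the 216. Three passages would still report power for a test that is not run, and SAP 4.6 would still state an alternative hypothesis that SAP 7.2.1 does not test. The defence supports the cheaper repair; it does not remove the contradiction.

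**Conclusion.** The concern holds and must be fixed before database lock. The sizing and analysis texts differ in the null value, and in SAP 4.6 also in direction. The stated 90% power belongs to a one-sided 5% test of 2 mmHg. The planned two-sided test of 0 has more than 99.9% power at the assumed effect and a pass mark of 1.34 instead of 3.12 mmHg. These figures rest on the plan's SD of 10 and on 216 analysed patients. The contradiction in the text depends on neither.

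**What to change.** The sponsor states which hypothesis is intended. Null, direction (reduction = Visit 2 minus Visit 4), sidedness and power are then made to agree in the synopsis, Protocol 12.2 and 12.5.2, SAP 4.6 and 7.2.1, and the DBP shell footnotes.

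**Least change: keep the two-sided test of 0.** In the synopsis, Protocol 12.2 and SAP 4.6, replace the 2 mmHg null with 0 and delete the greater-than-2 alternative. State that 216 patients give more than 99.9% power at 4 mmHg and SD 10, or 90% power for a true fall of 2.2 mmHg. This costs three paragraphs, with no new analysis or patients. It needs a protocol amendment under Protocol 12.6. It is not clearly a substantial one under 12.8, since the primary endpoint and analysis do not change, but the sponsor should also check it against the broader criteria in 12.6.

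**If 2 mmHg is the intended bar: test it.** Change Protocol 12.5.2 and SAP 7.2.1 and report the comparison with 0 descriptively. There are two versions:

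- Two-sided: the lower 95% limit for the reduction must exceed 2, and power is restated as about 83% in the three sizing paragraphs.
- One-sided 5%: the lower 90% limit must exceed 2, the 90% power stands, and the sizing paragraphs say one-sided.

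The null in the DBP footnotes of Tables 14.2.2.1 to 14.2.2.6 changes too, with a 90% interval row if one-sided. State the sign of the change-from-baseline row, because with Visit 4 minus Visit 2 the criterion becomes an upper limit below −2. Table 14.2.3.1 for systolic pressure reuses the 14.2.2.1 shell but keeps a null of 0 (SAP 7.3.1), so it needs its own footnote. This changes the primary analysis, so it needs a substantial amendment (Protocol 12 and 12.8) with ethics committee and authority approval, and it makes success harder.

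Raising the size to 265 is not worthwhile. It exceeds the Visit 2 cap of 2 × 110 = 220 (Protocol 5.1) and would need 265/0.75, about 354 screened, instead of 290. Restating the power costs no patients.

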screening visit. Patients previously receiving ZOF 30 mg or AML 5 mg will continue the same treatment, patients receiving other ACE-i will be switched to ZOF 30 mg, while patients receiving CCBs will receive AML 5 mg. Patients entering this phase in therapy with ZOF 30 mg or AML 5 mg should be in a 1:1 ratio. Assessment period from Visit 2 (Week 0) to Visit 4 (Week 8): patients having uncontrolled BP at Visit 2, will be assigned to the extemporaneous combination of ZOF 30 mg and AML 5 mg. After 4 Weeks \pm 2 days the BP will be assessed again (Visit 3): controlled patients (SBP/DBP ≤ 130/80 mmHg) will continue the same extemporaneous combination, while uncontrolled (SBP/DBP >130/80 mmHg) patients will be up-titrated from extemporaneous combination ZOF/AML 30/5 mg to extemporaneous combination of ZOF/AML 30/10 mg for further 4 weeks \pm 2 days (Visit 4, Week 8). At Visit 2 and Visit 3 patients with SBP/DBP value classified as Grade 3 (SBP \geq 180 or DBP \geq 110 mmHg) hypertension will be withdrawn from the study. *To be enrolled in the study, patients could be in monotherapy with one of the listed CCBs: felodipine, isradipine, lacidipine, lercanidipine, nicardipine, nifedipine, and nisoldipine. The primary endpoint will be assessed before and after assessment period at Week 8, by a paired t-test using the Intention-to-treat (ITT) Statistical population and the Per-Protocol (PP) population. Assumptions All the other continuous secondary/exploratory endpoints will be assessed before (Week 0) and after treatment (at Week 8) by a paired t-test. All secondary/exploratory endpoints related to proportion of patients achieving the BP goal at Week 4 and Week 8 will be analysed descriptively producing also the relative 95% CI to assess if there is a significant difference from Week 0 where all patients were uncontrolled.

[figure not shown]
немъни	Corporate Medical Department		
Identification Number	Version Number	State	Effective date
FORM-000050125	2.0, CURRENT	Effective	08, Jan 2021

Protocol Version 1.0 of 1 23/04/2021

Study Code: : MEIN/20/ZoAm-Hyp/001

A total sample size of 216 patients is required to achieve 90% power at a 5% significance level assuming a difference in mean DBP from baseline (Visit 2) to 8 weeks (Visit 4) of 4 mmHg and a standard deviation (SD) for this difference of 10 mmHg. The mean change in DBP for the null hypothesis is set equal to 2 mmHg.

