12 STATISTIC

This section outlines the major features of statistical analyses. More detailed methodology for summary and statistical analysis of data collected in this study will be documented in the statistical analysis plan (SAP), which will be maintained by the sponsor and completed prior to locking the database. The SAP may modify the plans outlined in the protocol; however, any major modifications of the primary endpoint definition and/or its analysis will also be reflected in a protocol amendment.

Any additional or supplemental data analyses performed independently by the investigator should be submitted to the Sponsor.

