### 5.3.3 Efficacy Population (EFF)

The Efficacy Population (EFF) is defined as all study participants in the Safety Population who complete the 4-week run-in period and meet continuation criteria at Visit 2 [uncontrolled BP (sitting SBP/DBP > 130/80 mmHg), tolerate treatment, and fall within 80-120% treatment adherence] and have at least one available post baseline primary efficacy assessment (from Visit 3 or 4). This population will be used for efficacy analyses.

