### 10 Summary of Changes to the Protocol

### 10.1 Analysis Populations

The Full Analysis Set (FAS) population was added to the SAP for its use to generate tables and listings related to enrollment and disposition.

The definition of the Efficacy Population (EFF) was slightly modified to include the enrollment continuation requirements at Visit 2 (uncontrolled BP, tolerate treatment, and 80-120% treatment adherence).

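### The primary analysis set is named inconsistently, and the unimputed Visit 2 to Visit 4 test leaves out patients withdrawn at Visit 3, so the estimated DBP fall may be biased

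*SAP*

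**What the plan says.** **Analysis set.** The synopsis (Statistical Assumptions) says the primary endpoint is assessed "by a paired t-test using the Intention-to-treat (ITT) Statistical population and the Per-Protocol (PP) population". No ITT set is defined in either document. Protocol 12.5.2 says "The Efficacy population will be used to analyse the primary endpoint". Protocol 12.3 defines that set as Safety-population patients who finish the run-in and have a Visit 2 BP, and limits each analysis to patients who have the data for it. SAP 5.3.3 adds the Visit 2 continuation criteria "and have at least one available post baseline primary efficacy assessment (from Visit 3 or 4"). SAP 10.1 reports only the first addition: the definition "was slightly modified to include the enrollment continuation requirements at Visit 2". In the table shells, Table 14.1.2 carries the SAP definition and Listing 16.2.3 still carries the protocol one.

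**Test and missing data.** SAP 7.2.1 tests a mean change of 0 mmHg, two-sided at 0.05: "The change from Baseline to Visit 4 values will be assessed using the paired t-test as described above". Under SAP 5.6.1, LOCF is for the sensitivity analysis only, and "No other standard imputations of missing efficacy data will be applied".

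**Who lacks a Visit 4 value.** Protocol 5 withdraws patients at Visit 3 for Grade 3 BP, intolerance, or adherence below 80% or above 120%. Protocol 10 treats data from later visits as missing. The same section and the flow chart text (2.2) ask for an early-termination visit with the Visit 4 assessments. SAP 5.2.4 tabulates early-termination visits but does not say which analysis visit they belong to.

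**The concern.** A patient withdrawn at Visit 3 with a BP reading that day belongs to EFF but has no Visit 2 to Visit 4 difference, so the primary test passes over that patient. For Grade 3 the recorded BP itself causes the withdrawal, so the missingness depends on the outcome. The Per-Protocol analysis has the same gap, because it requires all four visits.

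This is a single-arm study, so the mean change and its confidence interval are the result. If they describe only patients who stayed to Week 8, they answer a different question from the effect in everyone who started the combination. With three descriptions of the primary set in an open-label trial, and membership confirmed at a data review meeting before lock (SAP 5.3), the set should be settled in the text beforehand.

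**Working it through.** **1. The plan's own figure.** Inputs from Protocol 12.2: expected fall 4 mmHg, null 2 mmHg, SD 10, 5% level, 90% power. n = ((z_alpha + z_power) × SD / (4 − 2))². One-sided this gives 215 (216 with the t distribution; power at 216 is 90.1%). Two-sided it gives 263 (265 with t; power at 216 is 83.3%). So 216 reproduces as a one-sided calculation. Protocol 5 counts the 216 at entry to the assessment period, and neither document states an expected loss between Visits 2 and 4.

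**2. Bias in general.** Let d be the share of treated patients without a Visit 4 value, m_w their mean Visit 4 change had it been measured, and m_c the mean in completers. Overstatement of the fall = d × (m_w − m_c). With m_c = −4 and d and m_w assumed:

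| m_w | d = 5% | d = 10% |
|---|---|---|
| 0 | 0.05 × 4 = 0.2 | 0.10 × 4 = 0.4 |
| +5 | 0.05 × 9 = 0.45 | 0.10 × 9 = 0.9 |
| −8 | 0.05 × (−4) = −0.2 | 0.10 × (−4) = −0.4 |

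The last row is an understatement, as could happen if intolerance followed a large fall.

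**3. Grade 3 removal alone.** Simulation assumptions: Visit 2 DBP mean 90-97 and SD 6-7, kept between 80 and 110; change at Visit 3 mean −3, SD 10; change at Visit 4 mean −4, SD 10; correlation 0.5; removal if Visit 3 DBP is 110 or more.

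| Visit 2 mean (SD) | Removed | All treated | Completers | LOCF |
|---|---|---|---|---|
| 90 (6) | 2.5% | −3.99 | −4.26 | −3.71 |
| 92 (7) | 4.2% | −3.99 | −4.38 | −3.56 |
| 95 (7) | 6.5% | −3.99 | −4.57 | −3.39 |
| 97 (7) | 8.2% | −3.99 | −4.71 | −3.26 |

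Completers overstate the fall by about 0.3 to 0.7 mmHg. LOCF understates it by a similar amount, because it carries forward the extreme reading that triggered removal. A model using the Visit 3 change returns the all-treated value in each row, to within 0.01.

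With smaller visit-to-visit variation (true BP 142/88 to 152/95, SD 9/6), 0.4% to 2% are removed. The overstatement is then 5.976 − 5.957 = 0.02 to 5.214 − 5.121 = 0.09. Milder settings still bring it close to 0.

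**4. Leavers who had no benefit.** Simulation with true BP 142/88, SD 9/6, an assumed drug effect on DBP of −5.5 at Visit 4, and 10% leaving at Visit 3 without benefit:

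| Estimate | Mean change | Difference from all treated |
|---|---|---|
| All treated | −5.412 | – |
| Completers | −5.981 | 0.57 too large |
| Model using Visit 3 | −5.777 | 0.37 too large |
| LOCF | −5.366 | 0.05 too small |
| Zero change for leavers | −5.363 | 0.05 too small |

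At 5% the completers' overstatement is 0.29. The model removes 0.20 of 0.57, about a third.

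**5. Effect on the test.** With 25% lost after Visit 2, 162 completers remain, and two-sided power against 0 mmHg for a 4 mmHg fall is still above 99.9%. With 216 patients and 10% lost, the overall mean is 0.9 × (−4) + 0.1 × m_w and the variance is 100 + 0.09 × (m_w + 4)². Significance against 0 is lost only at m_w of about +19.6 (mean −1.64, SE 0.83, t = −1.97). Against the 2 mmHg sizing null it is lost at about +2.4 two-sided or +4.5 one-sided.

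**The case against.** Four stronger readings are tempting, and the documents do not support them.

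- **The SAP replaced an ITT analysis with a completers' t-test.** The synopsis itself specifies a paired t-test, and Protocol 12.5.2 already names the Efficacy population with a 0 mmHg two-sided null. The conflict starts inside the protocol. The undeclared post-baseline requirement removes nobody from the paired test, since a patient without Visit 4 BP has no difference under either definition. Whether it counts as a major modification under Protocol 12 is therefore arguable.
- **The DBP fall is overstated.** Only the Grade 3 mechanism has a clear direction. Withdrawal for intolerance or for adherence above 120% could act the other way, and no stated rate fixes the overall sign.
- **Visit 3 readings of withdrawn patients are thrown away, and early leavers are in no efficacy analysis.** Visit 3 values enter the LOCF analysis (Table 14.2.2.3) and the descriptive summaries (Table 14.2.1.1). Early leavers may have an early-termination BP. The gap is that no rule says whether it counts as Visit 4 or as post-baseline.
- **The trial's conclusion is at risk.** Against 0 mmHg it is not.

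The best remaining argument is that LOCF is already planned and, in step 4, comes closer to the all-treated value than the model does. That stands for leavers without benefit. In step 3 the order reverses: LOCF errs by as much as completers in the opposite direction, while the model is right. Neither is enough alone.

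**Conclusion.** The inconsistency is a matter of text and is certain: an undefined ITT set in the synopsis, the Efficacy population in Protocol 12.5.2 and the SAP, an incomplete declaration in SAP 10.1, and an outdated definition in Listing 16.2.3. It is also certain that the primary test, as written, omits patients withdrawn at Visit 3 unless an early-termination BP is assigned to Visit 4.

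The consequence is possible bias in the estimate and its confidence interval. Grade 3 removal overstates the fall by roughly 0 to 0.7 mmHg, depending on assumed BP level and variability. If 5-10% leave without benefit, the overstatement is about 0.2 to 0.6 mmHg. If leavers had larger falls than completers, the bias reverses. These sizes matter for describing the effect and for any statement against the 2 mmHg used in sizing. They do not matter for the planned test against 0. The point is worth settling before database lock, but it ranks below a must-fix.

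**What to change.** 1. Name one primary set, all patients who took at least one dose of the combination, in the synopsis, Protocol 12.3 and 12.5.2, SAP 5.3.3 and the shells (including Listing 16.2.3). List every change from the protocol definition in SAP 10.1.
2. State in SAP 5.2.4 whether an early-termination BP counts as Visit 3, as Visit 4 or as neither, and whether it meets a post-baseline requirement.
3. Make the primary estimate the Visit 4 mean from a repeated-measures model of change from Visit 2 at Visits 3 and 4, with visit, Visit 2 DBP and unstructured covariance. SAP 7.4.1 already uses a model of this kind. With complete data its Visit 4 mean matches that of the paired t-test.
4. Keep the paired t-test and LOCF as supportive. Add one row that gives zero change to treated patients without Visit 4 BP, because the model does not fully correct for leavers who had no benefit.

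The cost is a little more analysis work, extra rows in existing tables and a document amendment. Changing the primary estimate falls under the protocol's own rule that "any major modifications of the primary endpoint definition and/or its analysis will also be reflected in a protocol amendment". No new data or visits are needed, and the withdrawal rules stay as they are.
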